TCR is a physiological, life-threatening response with sudden onset of severe bradycardia, hypotension and asystole with parasympathetic activation of the heart due to stimulation of the vagal nerve as a result of stimulation of any of the three branches of the trigeminal nerve. (1). It is defined as a decrease in heart rate and mean arterial blood pressure by more than 20% from baseline or a heart rate of less than 60 beats per minute due to intraoperative traction or manipulation of the trigeminal nerve. The afferent branch of the trigeminocardiac reflex arc is formed by the sensory nerve endings of the fifth cranial nerve. Neuronal signals are sent to the trigeminal sensory nucleus via the Gasserian ganglion. The sensory nucleus of the afferent reflex branch of the trigeminal nerve connects to the efferent pathway via short internuncial fibres in the reticular formation with the more distant motor nucleus of the vagus nerve. Cardioinhibitory efferent fibres originate from the motor nucleus of the vagus nerve. It transmits vagus-mediated negative chronotropic and inotropic responses to the heart and terminates in the myocardium (5).

In the maxillofacial surgery literature, there are case reports reporting the development of trigeminocardiac reflex in orthognathic surgery, dental implant surgery and maxillofacial trauma surgery and prevalence studies for major surgeries (6,7,8). Haemodynamic changes and neurological-based emergencies (e.g. vasovagal syncope) are quite common in routine oral surgical procedures performed under local anaesthesia (9).

In addition, in a study, it was noted that a significant decrease in heart rate and blood pressure occurred during extraction of posterior mandibular teeth and this may be related to the trigeminocardiac reflex (10). Extraction of impacted wisdom teeth is one of the commonly performed procedures in the field of oral and maxillofacial surgery. To the best of our knowledge, there is no study in the literature evaluating the development of TCR during mandibular impacted wisdom tooth extraction.

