In the research arms we have established, the follow-up of TCR that may occur during the procedure will be provided by monitoring the patients (Contec Medical Systems, Hebei, China.) Heart rate, systolic and diastolic blood pressure, oxygen saturation will be recorded during the procedure. The records will be taken in 4 stages: before starting the surgical procedure, during the application of local anaesthesia, during the incision, during the elevation of the crown and root. Sudden changes that occur during the procedure will be recorded together with the process in which they occur.

(e.g. during local anesthesia)

Initial heart rate: 80 beats/min

End of procedure heart rate: 78 beats/min

Sudden presence of bradycardia or tachycardia during the procedure;

Sudden change in heart rate: 80>58 or 80>98)

During extraction of impacted wisdom teeth, a 20% decrease in heart rate and a decrease in heart rate below 60 will be considered as the development of TCR in parallel with the literature. The prevalence of TKR will be evaluated in 4 separate groups according to whether Gow-Gates anaesthesia or nervus alveolaris inferior anaesthesia is applied and whether the wisdom teeth are closer than 1 mm and 1 mm or further than 1 mm from the nervus alveolaris inferior.

During mandibular impacted wisdom tooth extraction, patients will be monitored and the following parameters will be evaluated:

1. Systolic blood pressure
2. Diastolic blood pressure
3. Oxygen saturation
4. Heart rate

The anxiety level of the patients will be assessed with the Amsterdam Preoperative Anxiety and Information Score Scale (APAIS) and State-Trait Anxiety Inventory (STAI-S) in order to differentiate TKR from common neurological emergencies (e.g. vasovagal syncope) due to dental phobia. State Anxiety Scale was developed in 1970 and its Turkish form was adapted in 1983 and validity and reliability study was conducted. APAIS was translated into Turkish for the first time in our country in 2007 and it was found that APAIS and STAI-S were correlated with each other in the studies conducted(11).

STAI-S (The State-Trait Anxiety Inventory)

Amsterdam Preoperative Anxiety and Information Scale (APAIS)

	Not all 1	2	3	4	Very much 5
I am worried about anesthetics					
The anesthetics is on my mind continually					
. I would like to know as much as possible about the anesthetic					
I am worried about the procedure.					
The procedure is on my mind continually.					

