Evaluation of results (Outcome/Endpoint)	
During extraction of impacted wisdom teeth, a 20% decrease in heart rate and a decrease in heart rate below 60 will be considered as the development of TCR in parallel with the literature. The prevalence of TKR will be evaluated in 4 separate groups according to whether Gow-Gates anaesthesia or nervus alveolaris inferior anaesthesia is applied and whether the wisdom teeth are closer than 1 mm and 1 mm or further than 1 mm from the nervus alveolaris inferior.
 
During mandibular impacted wisdom tooth extraction, patients will be monitorised and the following parameters will be evaluated:
 
 1. Systolic blood pressure 2. Diastolic blood pressure 3. Oxygen saturation 4. Heart rate 
Patients will be asked to fill out the Situational Anxiety Inventory (STAI-S) and the Amsterdam Preoperative Anxiety and Information Scale (APAIS) forms before the procedure in order to evaluate the relationship between the haemodynamic changes that may occur and anxiety..

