1	Kütahya Health Sciences University Faculty of Dentistry Oral, Dental and Maxillofacial Surgery	[name] [name]

Information for bioavailability/bioequivalence studies

Licence status	Not a bioavailability/bioequivalence study.
Analytical centre/department	Not a bioavailability/bioequivalence study.
Tested research product	Not a bioavailability/bioequivalence study.
Reference product	Not a bioavailability/bioequivalence study.
Study design	Not a bioavailability/bioequivalence study.
Working periods	Not a bioavailability/bioequivalence study.
Previous studies	Not a bioavailability/bioequivalence study.

Properties of active substance

Resolution	No active substance will be used.
Bioavailability	No active substance will be used.
AUC	No active substance will be used.
C_{max}	No active substance will be used.
t_{max}	No active substance will be used.
Elimination Half Life (t_{1/2})	No active substance will be used.
Volume of Dispersion	No active substance will be used.
Binding to Proteins	No active substance will be used.
Food Effect	No active substance will be used.
Metabolism and Metabolites	No active substance will be used.
Breakthrough	No active substance will be used.
Accumulation	No active substance will be used.
Blood collection times	No active substance will be used.
Substance covered by biosafety	No active substance will be used.
Intra-individual variability constant of the active substance (%CV)	No active substance will be used.
Substance to be analysed	No active substance will be used.

B. OTHER INFORMATION

Risk / Benefit evaluation

There were no risk factors related to the study.

In this study, the development of trigeminocardiac reflex, which is an important issue during the extraction of impacted wisdom teeth and can be life-threatening in some cases, will be evaluated and important information about the frequency of trigeminocardiac reflex will be obtained.

Sensitive population/Vulnerable Group (*Vulnerable subjects*)

No sensitive population/vulnerable groups.

Payment to volunteers

Volunteers will not receive any payment.

Volunteer services

Volunteers will not receive any payment..

Research / volunteer documents (*additional documentation and recruitment procedure*)

In the study, patient cards will be created to note the age, gender, distance of the mandibular impacted wisdom teeth to the nervus alveolaris, systolic-diastolic blood pressure, heart rate, oxygen saturation and changes in these during the procedure.

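### The TCR outcome rule counts any qualifying heart rate fall as TCR whatever its cause, and the pre-procedure anxiety scales named to separate vasovagal events cannot classify an event

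*Protocol*

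**What the plan says.** **Definition.** The Introduction-Purpose section, repeated under Purpose of the research, gives two haemodynamic routes to TCR. One is a fall of more than 20% in both heart rate and mean arterial pressure (MAP); the other is a heart rate under 60. Either must be "due to intraoperative traction or manipulation of the trigeminal nerve".

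**Outcome rule.** Materials and Methods, Scope of the research, and Evaluation of results (Outcome/Endpoint) all state, for the period of the extraction, that "a 20% decrease in heart rate and a decrease in heart rate below 60 will be considered as the development of TCR". The result is to be reported as TCR prevalence in four groups of 10.

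**Competing cause.** The Introduction says: "Haemodynamic changes and neurological-based emergencies (e.g. vasovagal syncope) are quite common in routine oral surgical procedures".

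**Anxiety scales.** Materials and Methods and Scope of the research say that APAIS and STAI-S are used "in order to differentiate TKR from common neurological emergencies (e.g. vasovagal syncope) due to dental phobia". Evaluation of results says that they are completed before the procedure and gives another purpose: "in order to evaluate the relationship between the haemodynamic changes that may occur and anxiety".

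**Timing.** Readings are taken "before starting the surgical procedure, during the application of local anaesthesia, during the incision, during the elevation of the crown and root". In addition, "Sudden changes that occur during the procedure will be recorded together with the process in which they occur".

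**Product.** The Risk / Benefit evaluation promises that "important information about the frequency of trigeminocardiac reflex will be obtained".

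**The concern.** The study asks whether TCR occurs in these extractions and how often. The main rival explanation for a sudden slow pulse in a dental chair is a vasovagal reaction, and the protocol says so itself. The rule that turns a heart rate trace into a TCR case asks only how far the rate fell and how low it went. It does not ask what was being done to the nerve, or whether the picture was vasovagal. The one safeguard the protocol names is measured before any event can happen.

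If the rule is followed as written, a qualifying vasovagal fall becomes a TCR case. The hypothesis is about occurrence, so a single mislabelled event could decide it. In a group of 10, one event moves the reported prevalence by 10 percentage points.

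**Working it through.** The protocol states no figure on this point that could be reproduced. The check compares its statements and then adds an illustration on assumed rates.

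**Step 1. Definition against rule.**

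| Element | Definition (Introduction; Purpose of the research) | Outcome rule (Materials and Methods; Scope; Evaluation of results) |
|---|---|---|
| Heart rate fall | more than 20%, together with MAP | 20% |
| MAP fall | more than 20%, together with heart rate | absent |
| Rate under 60 | sufficient as an alternative | required in addition |
| Cause: traction or manipulation of the nerve | required | absent |
| Timing | intraoperative | during extraction |

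The rule keeps a time window but no causal term and no exclusion of other causes.

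**Step 2. Can the scales supply the missing term?** Each patient has one pre-procedure score per scale. That score is the same for every heart rate event in that patient, so it cannot show whether a given fall was reflex or vasovagal. The protocol ties no score to the label of an event. The methods listed under Statistical Analysis compare, correlate or tabulate measurements; none classifies an event.

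**Step 3. Does the recorded stage supply it?** The stage of each sudden change is recorded, but the rule does not use it. The protocol's own example of a sudden change is set at local anaesthesia, with a rate going from 80 to 58. That is (80 − 58)/80 = 27.5% and below 60, so it meets both limbs. The text does not say whether an event at injection falls within the extraction period.

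**Step 4. What the joint threshold filters.** A 20% fall from 75 gives exactly 60, which is not below 60. From a baseline of 75 upwards, the below-60 limb therefore decides. Smallest qualifying falls in whole beats:

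- 70 to 56: 14/70 = 20.0%
- 75 to 59: 16/75 = 21.3%
- 80 to 59: 21/80 = 26.25%
- 90 to 59: 31/90 = 34.4%
- 100 to 59: 41/100 = 41.0%

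The filter works on depth of fall, not on cause.

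**Step 5. The rule also misses events.** A nerve-provoked fall from 90 to 65 is 25/90 = 27.8%. With a MAP fall above 20% it is TCR by the definition, but 65 is not below 60, so the rule does not count it. A nerve-provoked fall from 70 to 58 meets the definition's under-60 route, but 12/70 = 17.1% fails the 20% limb. Errors therefore run both ways.

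**Step 6. Illustration of false labels.** Let v be the risk per patient of a vasovagal fall that meets the rule, and suppose no TCR occurs. Every value of v is an assumption; the documents give none. Patients are taken as independent. The expected number labelled TCR is 40v, and the chance of at least one in n patients is 1 − (1 − v)^n.

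| v (assumed) | Expected in 40 | At least one in 40 | At least one in a group of 10 |
|---|---|---|---|
| 0.5% | 0.2 | 18% | 5% |
| 1% | 0.4 | 33% | 10% |
| 2% | 0.8 | 55% | 18% |
| 5% | 2.0 | 87% | 40% |
| 10% | 4.0 | 98.5% | 65% |

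**The case against.** **Cause cannot be read off a monitor.** Any working rule needs a proxy, and this one keeps a time window in a protocol that also records the stage of each event. That is fair, and it is why the remedy builds on the recorded stage. Timing alone, however, does not separate a reflex from a vasovagal reaction in the same stage.

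**A SAP could supply the link between score and event.** Cut-offs and derivations do often sit in a SAP, and none was available for this review. But the protocol itself fixes the outcome rule and itself gives the scales a differentiating role. No cut-off would turn a pre-procedure patient score into information about an event.

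**The threshold is strict and the illustration rests on assumed rates.** Both are true. The protocol's remark about frequency covers haemodynamic changes and emergencies in general, not falls that meet both limbs. The table shows sensitivity and is not evidence of how many events would be mislabelled.

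Three stronger readings are tempting, and the documents do not support them:

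- *A reader might infer that the count is an upper bound for TCR.* It is not: step 5 shows events that the definition admits and the rule leaves out.
- *A reader might infer that falls at injection are not TCR.* The documents do not settle this, and the protocol's own example is set at that stage.
- *A reader might infer that the protocol claims to have separated the two conditions.* It states a purpose for the scales, not that separation is achieved.

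**Conclusion.** The point holds on the text. The rule omits the causal condition in the protocol's own definition, and the only tool named for separating vasovagal events cannot classify an event. A vasovagal fall that meets both heart rate limbs during extraction is therefore counted as TCR and enters the reported prevalence.

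The size of the effect cannot be derived from the documents, since they give neither a vasovagal rate nor a TCR rate. The net direction of error is also unknown, because false inclusions and missed events pull opposite ways. The conclusion assumes that the two heart rate limbs apply jointly, as worded. The missing MAP term and the change from alternative to joint limbs matter here only because they rule out a one-sided bound; they are otherwise separate points.

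This should be corrected because the frequency of TCR is what the study sets out to deliver.

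**What to change.** 1. Report the rule-positive count as *heart rate events meeting the study threshold*, not as TCR prevalence without qualification. Do not call it an upper bound.
2. Tabulate these events by the stage already recorded: before surgery, injection, incision, crown and root elevation. Show injection-stage events separately, without ruling them out as TCR.
3. Add three fields per event to the patient card: whether manipulation was under way, symptoms including loss of consciousness, and treatment given. Show events with an evident vasovagal picture, and undetermined events, separately.
4. Describe APAIS and STAI-S as an association analysis, as Evaluation of results already does. Remove the differentiation statement from Materials and Methods and from Scope of the research.

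**Cost.** Wording changes, one table and three card fields, with no extra patients, staff or devices. The card fields must be in place before surgery, because some of this information cannot be recovered afterwards. The downside is that some events will remain undetermined and fewer will be called TCR.
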